Potentially eligible participants will be assessed via phone to determine whether they meet initial eligibility requirements. If eligible and interested, participants will be invited to Session 1 (pre Covid-19) or Session 2 (post Covid-19). They will be asked to abstain from smoking and all nicotine products (e.g., e-cigarettes) for 3 hours prior to attending this session, and told that confirmation of smoking status will be taken via a breath carbon monoxide (CO) measurement. There is no validated CO cut-off to confirm 3 hours of abstinence, so this is a “bogus pipeline” procedure, which has been found to improve accuracy of reported smoking behavior (Adams et al., 2008; Aguinis et al., 1993).

¹ Due to Covid-19 disruptions, after 3/13/20 additional safety precautions including minimizing participant contact were implemented. Aim 2 was powered for Session 2 (extinction), and cue reactivity was sufficiently demonstrated with the 17 participants who completed session 1 before the Covid-19 disruption in participant involvement. Thus, pre-Covid-19, participants attended both Sessions 1 and 2. Post-Covid-19, participants attend only Session 2 (extinction) and procedures were modified to accommodate a single session.

C.3.4. Procedure Overview for Session 1 and Session 2

At the beginning of Session 1 for pre-Covid-19 participants or Session 2 for post-covid participants, study staff will answer any questions the participants may have and the informed consent process will be completed. Participants will provide a breath CO sample and asked when they smoked their last cigarette, to confirm that they had abstained for 3 hours. Eligible participants will then complete a series of self-report questionnaires described below. We anticipate the informed consent and questionnaire phase will take approximately 45 minutes. Next, Session 1 pre-Covid-19 participants will complete the cue-reactivity procedures (about 45-60 minutes). Thus, Session 1 should take under 2 hours. Following this session, participants will be scheduled for Session 2 (extinction) within 120 days. Participants will be given similar pre-session abstinence instructions and asked to bring a pack of their own cigarettes. Again, this session will begin with self-report and CO assessment, and the full session is anticipated to last approximately 1.25 hours for pre-Covid-19 participants and 1.5-2.5 hours for post-Covid-19 participants.

If, at the beginning of either session, a participant self-reports smoking within the past 3 hours, s/he will be rescheduled. *Further, smoking status will be assessed at the beginning of Session 2; any participant who indicates that s/he has quit smoking for 24 hours or more will be ineligible for Session 2 (as participants will be asked to smoke during this session).* Otherwise, participants will then complete each respective session as described below. Participants will complete all procedures in a private laboratory room at TRIP. The procedures will be video-recorded from a central control room. The recordings will be reviewed to confirm study fidelity, and they will be used to score latency to smoke after Session 2.

C.3.5. Randomization

Session 1 will utilize a 2 x 2 within-subject design. Session 2 participants will be randomly assigned to either the extinction or control condition after stratifying by sex and cigarettes per day (cut point = 10). Block size will be 8 given the target sample size of 64 per condition (see below) and the 4 stratification cells.

C.3.6. Lab-based sessions: Descriptions of AR and In Vivo Cues

[figure not shown]
C.3.6.a. *AR Cues.* All AR cues will be presented via a smartphone provided to participants during the lab session. Six AR smoking cues and six AR neutral cues will be presented to participants. Although these cues can be presented individually (e.g., a single cigarette), we will have the ability to combine cues (e.g., cigarette in an ashtray). Further, movement of components of the cues (e.g., smoke coming up out of a cigarette, ash falling) will also be utilized whenever possible. Finally, participants will be encouraged to move around the stimuli to interact with the cue, as AR allows for the individual to see a stimulus from various angles. Urge to smoke and reality/co-existence questions will appear on the smartphone screen with response options. The AR app will allow for experimenters to select the order of the cues, as described below.

C.3.6.b. *In vivo Cues.* Presentation of in vivo cues will generally follow procedures used in the existing cue-reactivity literature (e.g., Wray et al. 2011; LaRowe et al., 2007). To match the AR cues for complexity and overall content, we will use 6 smoking and 6 neutral cues with matching content (e.g., if we use a pink eraser as a neutral cue for AR, a similar eraser will be used as an in vivo cue). Cues will be placed under numbered, opaque covers, and participants will be instructed when to uncover and re-cover each one during the trials. To control for assessment modality across Stimulus Type (AR vs in vivo), participants will answer urge questions via a smartphone app, similar to the AR app. Participants will also be encouraged to interact with the in vivo cues in a similar manner to the AR cues (e.g., walk around the cues to view from different distances and angles).

C.3.7. Session 1: Cue-reactivity

Session 1 will utilize a within-subjects design, so all participants will receive all cue presentations (see Figure 2 above). Because it would be difficult for participants to switch repeatedly between AR and in vivo cues, Stimulus Type (AR vs in vivo) will be presented in counterbalanced blocks. Within each block, we will randomize the presentation of smoking vs neutral cues. Figure 3 is a visual depiction of the stimulus-presentation strategy. Each cue will be presented for 15 seconds. Participants will complete the urge question at baseline and will then complete the urge question and reality/co-existence questions (for AR only) immediately following each cue presentation. To reduce carryover effects, each stimulus presentation will be

separated by 1 minute, during which participants will engage in a neutral activity (e.g., solving easy word search puzzles). The general procedures are similar to those commonly found within the literature (e.g., Carpenter et al., 2009; LaRowe et al., 2007; Wray et al., 2011). In sum, participants will complete baseline urge questions, view a cue for 15 seconds, complete urge and/or reality/co-existence questions, complete the word search for 1 minute, view another cue, and so on, until all 24 cues have been presented. The cue-reactivity procedures should last under 1 hour.

C.3.8. Session 2: Extinction

The extinction session will use only the AR cues (smoking and neutral). As noted above, participants will be randomized to either the extinction or control group. Twenty-eight trials of cues will be presented for each group. Both groups will receive the same neutral cue in Trial 1 (to establish baseline urge) and the same smoking cue in Trial 2 (for pre-test cue-reactivity). Then, the extinction group will receive smoking cues for trials 3-26, whereas the control group will receive neutral cues. Both groups will receive matched smoking cues for the second to last trial (27) followed by matched neutral cues for the final trial (28), for post-test cue-reactivity. Each cue will be presented for 1 minute and will be shown 4 times in trials 3-26. Figure 4 shows a visual representation of cue presentation for each group. With respect to the order of the cues, we will create 4 quasi-random orders for each condition (each comprising 4 blocks of 6 images, with no image repeated twice over a series of three images), which will be varied across participants. *We derived these procedures from the existing cue-exposure literature (e.g., Carpenter et al., 2009; Collins et al., 2011; Conklin & Tiffany, 2002; Kamboj et al., 2012; LaRowe et al., 2007; [name] et al., 2012), and although no specific guidelines exist, these studies typically exposed participants to cues for up to 60 minutes total (54 minutes in the current study); utilize one to nine cues (6 smoking and 6 neutral in the current study); and utilize various amounts of time for exposure to each individual cue, often ranging from 10 seconds to 5 minutes (1 minute in the current study). For this study, we wanted each cue to be presented multiple times to allow sufficient time and exposure for extinction to occur, which ultimately resulted in 28 trials.*

[figure not shown]

Figure 4: Session 2 Procedures
N = Neutral Cue; S = Smoking Cue; Dotted lines indicate paired cues

Following each cue, participants will complete the single-item measure of urge (primary outcome). Following the final trial (28) for both groups, participants will be presented with one of their own cigarettes and asked to take at least one puff. Latency to smoke will later be determined (using time stamps on the video-recording) and used as a secondary outcome as a behavioral measure of smoking motivation (e.g., Ditre et al., 2010; Kovacs et al., 2014; Shiffman et al., 2013; Stevenson et al., 2017). TRIP is equipped with 8 “negative pressure” rooms, compliant with state law regarding indoor smoking for research purposes that allow for the efficient removal of smoke between participants. Session 2 is expected to last 1.25 hours for pre-Covid-19 participants, and 1.5 to 2.5 hours for post-Covid-19 participants.

C.3.9. Compensation and Retention

Pre-Covid-19 participants will be compensated for Session 1 (\$40) and Session 2 (\$50). Post-Covid-19 participants will be compensated \$60 for Session 2. To aid in retention, the following procedures will take place: reminder phone calls prior to all study visits, flexible scheduling for sessions, reminder cards, requiring a functioning phone number and home address to contact participants by phone or mail as needed, and obtaining the name, address, and phone number of at least 2 collaterals (i.e., relatives, friends) who can provide contact information for the participants, should we be unable to reach them during the study.

C.3.10. Additional Measures

Aside from those already described, the following measures will be administered at Session 1 for pre-Covid-19 participants and at Session 2 for post-Covid-19 participants. *Demographics and Smoking History* will collect data on variables including gender, age, race, marital status, income, education, and smoking history (e.g., number of quit attempts, years smoked). *Fagerström Test for Nicotine Dependence* (FTND; Heatherton et al., 1991) is a widely used measure of nicotine dependence. *Wisconsin Smoking of Withdrawal Scale* (WSWS; Welsch et al., 1999) is a well-validated measure used to assess various facets of nicotine withdrawal. *Positive and Negative Affect Schedule* (PANAS; Watson et al., 1988) is a self-report measure that assesses an individual's positive and negative affect at a given point in time. We will also administer the *Brief Wisconsin Inventory of Smoking Dependence Motives* (WISDM-38), a multidimensional assessment of motivational factors associated with smoking behavior (Smith et al., 2010). We are particularly interested in the Cue Exposure/Associative Processes scale, which assesses the degree to which a participant's smoking is driven by cue-reactivity. Therefore, we will include the full subscale from the original WISDM-68 (Piper et al., 2014), due to its superior psychometrics (Smith et al., 2010). Aside from their descriptive value, these additional measures will allow for testing moderators of cue-reactivity and extinction.

Summary of Changes Pre and Post-Covid-19		
	Pre-Covid-19	Post-Covid-19
N	17	128
Session(s)	Session 1 and Session 2	Session 2 only
Consent and Survey administration (demographics, smoking history, etc.)	Session 1	Session 2
Length of Session(s)	1.25 hours	1.5-2.5 hours
Compensation	\$40 Session 1; \$50 Session 2	\$60

C.3.11. Data Management and Statistical Considerations

See Statistical Design and Power attachment, as per new instructions for Clinical Trial applications.

C.4. Aim 3: Initial Translation into Intervention-Ready App

C.4.1. Project Overview

Aim 3 will consist of the beginning phases of Stage II intervention development by (1) refining the app for intervention (rather than laboratory) use, (2) pilot testing the app for utility and acceptability in the smokers' natural environment, and (3) examining proxies of behavior change for quitting smoking and smoking status. Although we will use the same general components of the app developed for Aim 2, we anticipate that improvements to the app will be necessary to enhance its sophistication and usability by smokers attempting to quit in the field. When Aim 3 is complete, we expect the app and study team to be ready to conduct a fully-powered, randomized controlled trial using AR as an adjuvant therapy for smoking cessation. Finally, given the rapid pace of technology, it is very possible that by the time of Aim 2 completion, AR headsets/eyewear will be available at a reasonable cost. (Note that AR contact lenses are also under development.) If so, we will also pilot test these AR systems for utility and acceptability as part of Aim 3.

C.4.2. App Refinement

We will work with our AR software developers to refine the app based on (1) experimenter observation and participant feedback from Aim 2; (2) advances in AR capabilities since Aim 1; and (3) additional requirements for field use. In terms of the last, the app will be adjusted to deliver the cues over a longer period of time, as described below, and modified to allow bidirectional data transfer between the device in the field and the lab. This will allow the research team to alter or correct stimulus presentation, if necessary, and to download data on app use and response variables at regular intervals. We will also be able to add additional AR smoking cues, including distal cues (e.g., alcohol, coffee), which have been shown to be potent precipitators of smoking urge and relapse (e.g., [name] et al., 1990; Conklin et al., 2008). Other user-friendly modifications will also be made (e.g., colors, fonts). Finally, versions of the app will be created for both IOS and Android operating systems, which will capture the vast majority of smokers.

C.4.3. Participants and Recruitment

We will recruit a small group of participants ($N=50$) using similar strategies and inclusion/exclusion criteria as Aim 1. *However, additional inclusion criteria will be having a smartphone that they are willing to use during the study, and being motivated to quit smoking within the next month (i.e., “preparation” stage of the Transtheoretical Model; Prochaska et al., 1992).* Because participation will be entirely remote, participants will not need to have a local address. If deemed eligible, they will be asked to provide verbal informed consent via telephone or video conferencing.

C.4.4 Procedures

After consenting, enrolled participants will be sent a link to complete an online baseline survey. Once the completed baseline survey has been returned, the participants will be sent a code or instructions to download the free app. They will also be sent a user/training manual for the AR app use. *Given that all participants will be motivated to quit smoking, basic cessation assistance will be provided, including Tobacco Free Florida’s Quit Tips smoking cessation manual and the FL state tobacco quitline phone number and website.* A few days after the app and quitting materials are sent, research staff will call participants to explain the materials and answer questions. Participants will be instructed to use the AR app over the next 7 days in locations and situations where they smoke (e.g., home, bar; see Figure 5), with the goal of at least 5 uses per day. Usage and rating data will be collected in real-time. After the 7-day app use period, participants will be sent a link to an online follow-up survey that includes feedback on the app, smoking within the prior 7 days and smoking cessation motivation. Within approximately 7-14 days of completing the 7 day app use, participants will complete a brief telephone interview with study staff on their perceptions of the app as a potential cessation adjuvant and cigarette use over the course of the study. Participants will be compensated with electronic gift cards with value totaling up to \$80. Participants will receive \$10 for each of the completed baseline and follow-up surveys and the follow up phone interview. Participants can also receive a bonus of \$5 for each online survey completed within 24 hours of being sent the link and a bonus of \$5 if the follow up phone interview is completed within 10 days of completing the app use period. Participants will also receive \$5 for each day that they use the AR app at least one time (for up to \$35). Participants must use the app on at least four occasions to be eligible for the follow-up survey and interview.

C.4.5. Measures

To assess usability and acceptability, we will use both an established questionnaire, as well as questions developed for this study. Questions developed for this Aim are derived from [name] experience with implementing mHealth procedures among smokers, as well as the existing literature on usability testing (e.g., Harrison et al., 2013; Nayebi et al., 2012). We will also track how often participants use the app over the course of the week. The *System Usability Scale* measures participants’ perception of usability and learnability (Brooke et al., 1996; Lewis & Sauro, 2009). To assess other components of usability and acceptability, we will develop a questionnaire with Likert scale items to capture the following areas: *reality/co-existence* (same items as in Aims 1 and 2), *usefulness* (Would this app appeal to you if you were currently attempting to quit smoking?), *ease of use* (How easy/difficult did you find using the app?);, *ease of learning* (How many days did it take to get comfortable using the app?); and *satisfaction* (Would you recommend this app to a friend or family member to help them quit smoking?; Overall, how satisfied were you with the app?).

Participants will also be asked questions by a trained interviewer on their perceptions of the phone app as a potential adjuvant for smoking cessation. Specifically, participants will be queried with open-ended questions such as, “What type of changes would you make to the app to increase the likelihood of using it, or, to make it more enjoyable to use?; What features would you add to the app?; What was the easiest part of using the app?; What was the most difficult part of using the app?; What was the most interesting part of using

[figure not shown]

Figure 5: Simulated examples of AR stimuli in a smoker’s home setting, including a single stimulus (left) and a three-object compound stimulus (right).

the app?”. These interviews will be recorded, transcribed and coded for analysis (described in more detail in the Statistical Design attachment).

Proxies of behavior change will be collected pre- and post-app testing, including motivation to quit and self-efficacy for quitting. For motivation, we will use the Contemplation Ladder, which provides a visual image of a 10-rung ladder for participants to indicate their current motivation to change their smoking behavior (Biener & Abrams, 1991). We will also use the short form of the Abstinence-Related Motivational Engagement scale (ARME; Simmons et al., 2010), which provides a more sensitive index of current motivation. For self-efficacy, we will use the short form of the Self-efficacy Scale—Smoking, which is a 9-item measure that determines an individual’s level of confidence for not smoking in positive/social situations, negative affect situations, and out of habit (Velicer et al., 1990).

Data on smoking urges and smoking status will also be collected. Throughout testing, participants will rate their urge to smoke each time they use the app, which will allow us to observe any changes over time in this variable. Smoking status will be collected daily on the app and at follow-up, and abstinence will be defined as a self-report of no smoking in the past seven days (Perkins et al., 2013). Given the limited-time frame of this grant, we will only have short-term abstinence outcomes (7 days post-quit).

C.4.6. Statistical Considerations

See Statistical Design and Power attachment, as per new instructions for Clinical Trial applications.

C.5. Design Considerations

Choice of Comparison Stimuli Type for Aim 2, Session 1. Laboratory studies have historically used a variety of modalities for presenting cues to participants including in vivo, imaginal, video, photos, and audio (Conklin & Perkins, 2002). For this proof-of-concept study, we chose to compare the AR cues to *in vivo* cues for two reasons. First, *in vivo* cues are one of the most commonly used cues in the cue-reactivity literature (Conklin & Perkins, 2002). Second, using *in vivo* smoking cues sets the bar high for the AR comparison group, as they are the cues that smokers would typically see in their natural environment. Indeed, all other cue modalities are attempts at approximating *in vivo* cues. Thus, we believe comparing AR to real-world stimuli is ideal. Evidence that AR cues produce similar reactivity as do *in vivo* cues will provide strong support for this program of research.

Temporality of Session 1 (cue-reactivity test) and Session 2 (extinction test). We considered two options for these two critical proof-of-concept tests of AR stimuli. We could have conducted these as two separate, sequential studies, using different participants, with the second study dependent on findings from the first. The primary advantage would be the possibility of making major revisions to the AR app based on findings from the first study prior to conducting the second. However, sequential studies would have required a much longer time frame and the recruitment of many more participants, which presents challenges with respect to this grant mechanism. Therefore, we opted to conduct the two tests simultaneously for each participant (as two sessions), using the same research participants. This decision was bolstered by our high degree of confidence based on the existing cue-reactivity literature that AR stimuli will produce significant cue-reactivity. Despite this confidence, we believe it is necessary in a systematic line of research to subject this confidence to an empirical, documented test. Moreover, using the same participant sample allows us to use data collected in Session 1 (e.g., cue-reactivity, reality/in-presence) as moderator variables in Session 2.

Three-Hour Period of Abstinence. For both studies in Aim 2, we will ask participants to refrain from smoking for 3 hours prior to the session and will rely on self-report of no smoking to gauge compliance, along with “bogus-pipeline” collection of breath CO. These decisions were made for multiple reasons. First, because participants will have a range of smoking dependence, there are no valid CO cut-points to verify abstinence within the past 3 hours. We considered adding an initial session to collect baseline CO, but this would entail participants attending 3 sessions, which would increase attrition. Second, we could have asked for overnight abstinence and confirmed abstinence with CO the following day. However, again, due to the variability in smoking dependence, CO would not be accurately captured among light smokers. Compliance with overnight abstinence would likely be lower, and we would have less flexibility for scheduling the experimental sessions. Further, the bogus pipeline of CO should further increase compliance. Third, cue-reactivity is often elevated during acute deprivation, and 3 hours of abstinence should demonstrate substantial increases in craving/withdrawal (Hendricks et al., 2006).

Modality for AR presentation. The current study will evaluate cue-reactivity and extinction via a smartphone. We also considered using headgear/eyewear (i.e., AR glasses) as another modality. On the one hand, eyewear should allow the participant to be more immersed in his/her environment with greater co-existence. However, at this time AR eyewear is extremely expensive and less scalable than if we present AR via smartphone. As such, we decided to begin this line of research using a smartphone, with the intention of testing eyewear in the future, as the technology advances and the price drops.

Go vs No-Go Thresholds and Alternative Strategies. Aims 1 and 3 are developmental in nature and already have a built-in iterative process that allows us to incorporate feedback from participants and address potential issues as they arise. It is possible that Aim 2 might not result in the hypothesized cue reactivity and extinction, limiting our ability to advance to Aim 3. Although we do not anticipate this occurring due to the strong theoretical and empirical foundation of Aim 2, if this does happen, we will explore potential reasons for the unexpected outcomes (e.g., number of trials, reality/co-existence outcomes), including examination of the potential moderator variables. Based on those findings, we will modify the protocol (e.g., increase number of trials) and retest the key elements on new participants. Although we believe this is unlikely, if necessary we would defer Aim 3 in favor of resolving problems with Aim 2.

C.6. Timeline

Please see Study Timeline attachment, as per new instructions for Clinical Trial applications.

C.7. Implications and Future Directions

The primary goal of this study is to validate AR as an effective way to present smoking stimuli to elicit cue-reactivity and subsequent extinction. If successful, these findings have immediate implications for the use of cue-exposure as an adjunct to smoking cessation treatment. Indeed, AR has the potential to solve the extinction generalizability challenge presented by the renewal effect, which has limited the potential of cue-exposure treatments to date. Next steps would include taking our extinction paradigm into the real-world and conducting a larger, randomized controlled trial testing the efficacy of adding AR cue-exposure to an existing evidence-based smoking cessation program. Although the current study examines smoking stimuli (i.e., proximal cues), future research can also evaluate the role of AR for extinction of urge provoked by distal cues (e.g., alcohol, coffee; Conklin et al., 2008), which are also potent precipitants of smoking relapse. Beyond cue-exposure treatment, AR stimuli could be incorporated into other intervention protocols (e.g., coping skills training; mindfulness). This research could also inform the development of treatments for other mental health conditions that utilize extinction as part of treatment (e.g., other substance use disorders, social anxiety, PTSD). Exploring potential moderators (e.g., sex, nicotine dependence, initial cue-reactivity) will also allow us the ability to determine for whom this type of treatment may be most efficacious, consistent with a personalized medicine approach for treatment.

C.8. Participant Confidentiality

In the event, and only in the event, that study staff must work from home due to mandated orders (e.g., COVID-19 stay home orders), documents that contain protected health information may be temporarily kept at a personal residence for data entry and analysis. Documents will be secured in such a manner that they will be protected from being accessed by other individuals and pets who live in or visit the home. Any remote meetings (e.g., zoom meeting) or conference calls where protected health information may be discussed will be performed in a location that does not have listening devices (e.g., amazon echo) and are not likely to be overheard by those who live in or visit the personal residence.

REFERENCES

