The 2x2 within-subject design for Session 1 will provide measures of urge to smoke and reality/co-existence (for AR only) for analysis. Smoking cue-reactivity will be computed for both the AR and the in vivo conditions by subtracting the average urge to smoke (1-10 scale) following smoking cues from the average urge to smoke following neutral cues; higher scores represent greater smoking cue-reactivity. Based on the existing literature (Carter & Tiffany, 1999), we expect in vivo smoking cue-reactivity equivalent to a Cohen's $d = 1.0$, a very large effect. In terms of urge to smoke, this approximates an average difference score of 2.0 units with a standard deviation of 2.0.

Support for the effectiveness of AR to generate smoking cue-reactivity will be evaluated in two ways. First, average AR smoking cue-reactivity will be tested against a minimal threshold of Cohen's $d = 0.5$ (i.e., expected 1 unit on the urge to smoke scale) using a single-sample t-test. Second, the equivalence of the AR and in vivo stimuli toward generating smoking cue-reactivity will be evaluated using two one-sided tests (TOST) for equivalence.

The 142 participants completing Session 1 will be randomly assigned to the extinction or control condition in Session 2. With an estimated attrition of 10%, 128 are expected to complete Session 2. One measure of extinction will be the difference in urge to smoke at Trial 27 from urge to smoke at Trial 2, such that more positive values represent greater extinction of AR smoking cue-reactivity. Extinction based on this measure will be evaluated using a between-groups t-test. In addition, growth curve modeling will be used to compare the trajectories of urge to smoke using each self-report during the presentation of stimuli with the hypothesis of a greater negative slope for the extinction condition. Finally, the secondary measure of latency to smoke following the extinction trials will also be evaluated using a between groups t-test.

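### Session 2 is randomised within sex by cigarettes-per-day strata, but both planned t-tests leave the strata out, so they are somewhat conservative to the extent that the strata predict the outcome

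*Combined protocol and SAP*

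**What the plan says.** **Allocation (C.3.5. Randomization).** Session 2 participants are assigned at random to extinction or control "after stratifying by sex and cigarettes per day (cut point = 10"). The block size follows: "Block size will be 8 given the target sample size of 64 per condition (see below) and the 4 stratification cells".

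**Analysis (Statistical Design and Power, Aim 2).** Three Session 2 comparisons are described, and none mentions the stratification factors:

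- The extinction score is a within-person difference between urge at Trial 2 and urge at Trial 27: "Extinction based on this measure will be evaluated using a between-groups t-test".
- For trajectories, "growth curve modeling will be used to compare the trajectories of urge to smoke using each self-report during the presentation of stimuli". The hypothesis concerns the slope. No covariate list is given.
- For latency, "the secondary measure of latency to smoke following the extinction trials will also be evaluated using a between groups t-test".

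The power statement in the same section is for the plain t-test: 64 per condition, two-sided alpha .05, d of .50 or more, power at least .80. Sex enters a model only in the exploratory moderator analyses, as a Group by Sex interaction. Cigarettes per day is named in no model.

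**The concern.** Stratified blocks force the arms to be nearly balanced on the four cells, so differences between strata contribute almost nothing to the observed difference between arms. A plain two-sample t-test does not use this. Its error term is the total within-arm variance, which still contains the between-stratum part. If the strata are related to the outcome, the standard error is then larger than the true sampling variability of the group difference. Intervals are too wide, and the test rejects a true null less often than its nominal 5%.

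What is at stake is precision in the powered comparison of Session 2 and in the latency comparison. Section C.5 makes progress to Aim 3 depend on the Aim 2 results, so it is reasonable to use the precision that the design already provides.

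**Working it through.** **Inputs from the documents.** 64 per condition, two-sided alpha .05 and d = .50 (Statistical Design and Power, Aim 2); four strata and blocks of 8 (C.3.5).

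**Assumed input.** R², the share of outcome variance explained by the four strata. The documents give no value, so a range is shown.

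**Step 1: reproduce the stated power.** The noncentrality is 0.5 × √(64/2) = 2.83. With 126 degrees of freedom the noncentral t gives power .801, which agrees with the stated figure of at least .80.

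**Step 2: size of the unadjusted test.** Take the total outcome variance as 1. With arms balanced inside each stratum, the true variance of the group difference is (1 − R²) × 2/64, while the t-test estimates it as about 2/64. The standard error is therefore too large by the factor 1/√(1 − R²), and

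actual alpha = 2 × [1 − Φ(1.96/√(1 − R²))].

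For R² = .10, 1.96/√.90 = 2.066, which gives .039.

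**Step 3: power at d = .50, both ways, at the same R².**

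- Unadjusted: 1 − Φ{[t(.975, 126) × √(2/64) − 0.5] / √[(1 − R²) × 2/64]}.
- Adjusted: noncentral t with effect 0.5/√(1 − R²), 64 per arm and 128 − 5 = 123 degrees of freedom.

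| Assumed R² | Actual alpha, unadjusted | Standard error too large by | Power, unadjusted | Power, adjusted |
|---|---|---|---|---|
| 0 | .050 | 0% | .802 | .801 |
| .02 | .048 | 1.0% | .805 | .809 |
| .05 | .044 | 2.6% | .808 | .821 |
| .10 | .039 | 5.4% | .815 | .841 |

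(The unadjusted column uses a normal approximation, hence .802 rather than .801 at R² = 0.) The gain in power from adjusting is .809 − .805, .821 − .808 and .841 − .815, or roughly 0.4, 1.3 and 2.6 percentage points.

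**Step 4: check by simulation.** The set-up was permuted blocks of 8 in four strata, 128 participants and 20,000 null runs per value. At R² = .10 the size was .040 unadjusted and .051 adjusted. At R² = .05 it was .045 and .051. At R² = .02 it was .052 and .055, so the simulation does not separately confirm the .048 at that value, where the effect is negligible in any case.

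**Step 5: the growth curve.** Per-person slopes over 28 trials were compared between arms without strata (12,000 runs). When the strata explained 20% of the variance in urge level and none in slope, the size was .049. When they explained 10% of the slope variance, it was .038. Only strata that predict slope matter for the slope hypothesis.

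**The case against.** The best counter-argument is that the effect is conditional and may be very small. Several parts of it stand.

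- **No evidence that the strata are prognostic.** C.3.5 gives no reason for choosing the two factors. The moderator paragraph names sex as a possible modifier of the group effect, which is not the same as predicting the outcome, and it names nicotine dependence rather than cigarettes per day. A reader might infer that the tests are known to run below .05. The documents do not support that, because at R² = 0 the size is exactly nominal.
- **The extinction outcome is a change score.** A stratum effect on urge that is equal at Trials 2 and 27 cancels. Only strata that predict change matter, so a low R² is plausible for the powered test. Latency has no such protection: it is a single measurement after the session, and any stratum effect enters its error term in full.
- **The growth-curve model is unspecified.** A reader might infer that the plan excludes the strata from it. The text is silent on covariates, and silence is not exclusion.
- **Nothing promised is lost.** A reader might infer a shortfall in power. Unadjusted power stays at about .80 or above across the range, because stratified allocation helps the plain t-test somewhat too. The fair comparison is adjusted against unadjusted at the same R², not adjusted against .80.

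The objection does not remove the basic mismatch: the allocation uses the strata and the two t-tests do not, although including them costs almost nothing.

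**Conclusion.** The omission is real for both t-tests, and its consequence is conditional. To the extent that sex and the cigarettes-per-day cut predict the change score or latency, the standard errors are too large and the tests are conservative. The size of the effect rests wholly on an assumed R². At values of .02 to .10, the standard error is overstated by about 1% to 5.4%, alpha falls from .05 to between .048 and .039, and at most about 2.6 points of power are left unused. These figures also assume near-balance of the arms within strata.

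The group difference is not biased, false positives are not inflated, and the stated power is not undercut. For the growth curve the point is one of specification: the slope comparison is affected only if the strata predict slope, and the covariates are not yet stated. This is a modest improvement to efficiency and calibration at no real cost, not a threat to the study's conclusions.

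**What to change.** In Statistical Design and Power, Aim 2:

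- Replace both between-groups t-tests with a linear model of the outcome on group plus the randomisation strata (sex and the cigarettes-per-day cut, entered as the four cells). Take the group effect and its confidence interval from that model.
- State the covariates of the growth-curve model, and include both stratum and stratum-by-time terms. Stratum main effects alone would not absorb differences in slope between strata.

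The cost is a sentence or two of text. Both factors must already be recorded in order to randomise, so no new data are needed. If the strata prove uninformative, about 3 of 126 degrees of freedom are spent and power is .801 either way. The existing sample-size statement can stand as it is.
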